Transcranial alternating current brain stimulation (tACS), is a neurophysiological method of non-invasive modulation of the excitability of the central nervous system that is having an increasingly numerous spectrum of potential therapeutic applications. Recent studies have demonstrated the effectiveness of this method in modulating the natural frequencies of cerebral oscillation, underlying multiple cognitive processes such as verbal memory, perception and working memory.

On the basis of these premises, the treatment with gamma tACS is proposed in patients affected by Alzheimer's disease.

In this randomized, double-blind, sham-controlled, cross-over study, the investigators will evaluate whether a single stimulation with gamma tACS on the posterior parietal cortex can improve symptoms in patients with Mild Cognitive Impairment due to Alzheimer's disease.

Presidio Ospedaliero
di Brescia

Sistema Socio Sanitario

Regione
Lombardia

ASST Spedali Civili

Università
degli Studi
di Brescia

CLINICA NEUROLOGICA - UNIVERSITA' DEGLI STUDI DI BRESCIA
UO Neurologia 2 - AZIENDA SOCIO SANITARIA TERRITORIALE degli SPEDALI CIVILI DI BRESCIA
Direttore: [name]

Subjects will be randomized in two groups, one receiving a single treatment with gamma tACS (40 Hz) first and the other receiving sham stimulation. After one week the treatments will be exchanged. Patients will be evaluated with neuropsychological tests and neurophysiological measures of cholinergic transmission.

OBJECTIVES: The aim of the study is to evaluate the effects on cognitive performance of tACS in patients suffering from Alzheimer's disease (AD) to identify a possible rehabilitation protocol. The effect of tACS on intracortical connectivity will also be evaluated using the and SAI TMS protocols.

PROCEDURES: Patients followed at the Neurological Clinic with a diagnosis of Alzheimer's disease will be enrolled according to current clinical criteria. Patients will be randomized into two groups:

The first group will undergo a stimulation protocol by means of tACS (real), the second group will undergo a placebo treatment (sham).

Treatment group:

Each session will consist in the application of a tACS session (real at 3 mA) at the cortical level for the duration of 60 minutes each, during which patients will be subjected to an experimental cognitive task (Face Naming Task). The pre- and post-stimulation effects with tACS will be evaluated; in particular, the effects on cognitive performance will be assessed through the use of dedicated tests (Rey Auditory Verbal Learning Test - RAVLT) and the effects on the neurophysiological parameters of SAI using TMS.

Placebo group:

In the placebo group, the assembly will be kept the same as that of the real stimulation, however the electric current will be automatically interrupted about 5 seconds after the start of the stimulation, so as to make the placebo stimulation indistinguishable from the real one. The same tests and assessments used during real stimulation will be used.

After 1 week (after a single session of real stimulation or placebo stimulation) the two groups will be inverted (cross over).

INCLUSION CRITERIA:

- Mild Cognitive Impairment due to Alzheimer's disease (according to Albert et al., *Alzheimers Dement* 2011).

Presidio Ospedaliero
di Brescia

Sistema Socio Sanitario

Regione
Lombardia

ASST Spedali Civili

Università
degli Studi
di Brescia

CLINICA NEUROLOGICA - UNIVERSITA' DEGLI STUDI DI BRESCIA
UO Neurologia 2 - AZIENDA SOCIO SANITARIA TERRITORIALE degli SPEDALI CIVILI DI BRESCIA
Direttore: [name]

EXCLUSION CRITERIA:

- Cerebrovascular disorders, previous stroke, hydrocephalus, and intra-cranial mass documented by MRI.
- History of traumatic brain injury or other neurological diseases.
- Serious medical illness other than FTD
- History of seizures
- Pregnancy
- Metal implants in the head (except dental fillings)
- Electronic implants (i.e. pace-maker, implanted medical pump)
- Age <18 years

STUDY DESIGN: this is a placebo-controlled, randomized, double-blind, non-pharmacological interventional clinical trial, as neither the patients nor the person who will administer the evaluation tests will be aware of the type of treatment performed, real-tACS or placebo (tACS: placebo tACS = 1 : 1). This is a crossover study, in fact the patients who will carry out the first real stimulation session will carry out a second session with placebo stimulation after 1 week and vice versa. An experimental task (Face Naming Task) will be performed in both sessions.

In consideration of the transient effects of tACS, with a duration of cognitive effects of a few hours after the interruption of stimulation, the study does not provide a long-term follow-up.

Patients diagnosed with Alzheimer's Disease will be included. Each patient will undergo a cognitive assessment with the administration of a dedicated test (Rey Auditory Verbal Learning Test - RAVLT) and analysis of neurophysiological parameters of SAI by TMS before treatment and immediately after. All measures will be repeated after a week by reversing the stimulation from real to placebo and vice versa. In both sessions, a task, the Face Naming Task, will be carried out during the stimulation with tACS, both real and placebo.

END POINTS: The effect of tACS alternating current brain stimulation on the Face Naming Task and RAVLT will be primary outcome measures. The effect of tCAS on SAI measures will be considered as secondary outcome measure.

STATISTICAL PLAN: we will use parametric analyzes (t test) to compare the demographic variables (age and education) of the two groups at baseline. A $p < 0.05$ will be considered significant. To evaluate the effect of the stimulation protocol using tACS on cognitive performance we will use an ANOVA model.

Power analysis: considering that similar studies have not been published, we used data from slightly different studies (both by population and by method of stimulation),

Presidio Ospedaliero
di Brescia

Sistema Socio Sanitario

Regione
Lombardia

ASST Spedali Civili

Università
degli Studi
di Brescia

CLINICA NEUROLOGICA - UNIVERSITA' DEGLI STUDI DI BRESCIA
UO Neurologia 2 - AZIENDA SOCIO SANITARIA TERRITORIALE degli SPEDALI CIVILI DI BRESCIA
Direttore: [name]

always remaining within the established safety limits (Antal 2017). The "effect size" $f(V)$ was calculated using the direct method. Taking into consideration from the aforementioned studies an effect size equal to a partial η^2 of 0.205, equal to an "effect size" $f(V)$ of 0.5078 and, considering $\alpha = 0.05$ and the power $(1-\beta) = 0.80$, the expected sample size is 18 subjects using a repeated measures ANOVA study with two within-subjects factors: both treatment (real vs placebo - crossover study) and time (T0 and T1). The proposed sample size of 20 subjects should be adequate to achieve the main objective of the study.

ETHICAL CONSIDERATIONS (RISK-BENEFIT): tACS is a non-invasive, low-cost and simple to perform method that is having a growing diffusion and an ever-increasing spectrum of potential therapeutic applications.

We hypothesize that tACS can have a positive effect on naming performances in patients suffering from neurodegenerative diseases, such as Alzheimer's disease and frontotemporal dementia, and that tACS can have a positive effect on the normalization of neurophysiological parameters that have been altered in subjects affected by these diseases. neurodegenerative, for which there is still no treatment.

Literature data show that the application of the method according to the current safety guidelines (Iyer, 2005; Nitsche, 2003; Wassermann 2005; Antal 2017) has little relevant side effects, including mild tingling sensation during or after stimulation, moderate fatigue, mild itching sensation at the electrode application points, mild burning or pain, headache, nervousness, nausea, blistering at the electrode application points in more rare cases.

As for the TMS method, it is a non-invasive brain stimulation that allows the study of neurophysiological parameters that can provide information on the pathophysiological mechanisms involved in neurodegenerative pathologies.

Literature data show that the application of the method according to the current safety guidelines has minor side effects: a certain number of subjects participating in TMS experiments (up to 20%) suffer from headache or back pain, due to likely to excessive muscle tension and stiff head and / or neck position during TMS application. These effects are temporary and in most cases do not require any treatment.

Since TMS produces a magnetic field, people with fixed electrical stimulators (e.g. heart stimulators, nerve stimulators, hearing implants) that would not function or be damaged by the magnetic field cannot participate in the study. Also excluded from the examination are those with particular metal foreign bodies (for example splinters, some prostheses, screws and nails) that could move if placed within the magnetic field. Because the effects of TMS on the developing fetus are not known, pregnant women cannot participate in the study.

CLINICA NEUROLOGICA - UNIVERSITA' DEGLI STUDI DI BRESCIA
UO Neurologia 2 - AZIENDA SOCIO SANITARIA TERRITORIALE degli SPEDALI CIVILI DI BRESCIA
Direttore: [name]

PERSONAL DATA PROCESSING:

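### The plan repeats RAVLT and the Face Naming Task within about a week without calling for alternate forms, so item learning can add variance and, if retention depends on treatment, bias Face Naming towards no effect

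*Combined protocol and SAP*

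**What the plan says.** Under END POINTS, the effects "on the Face Naming Task and RAVLT will be primary outcome measures". STUDY DESIGN places RAVLT before and immediately after stimulation in each session, and adds: "All measures will be repeated after a week by reversing the stimulation from real to placebo and vice versa". Face naming is placed differently: "In both sessions, a task, the Face Naming Task, will be carried out during the stimulation with tACS, both real and placebo". No pre-stimulation face-naming score is described.

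On test material, PROCEDURES (Placebo group) says only "The same tests and assessments used during real stimulation will be used". Parallel word lists, alternate face sets and form order are not mentioned anywhere.

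The sessions are one week apart and order is randomised 1:1. The one statement on duration, in STUDY DESIGN, is that tACS effects are transient, "with a duration of cognitive effects of a few hours after the interruption of stimulation". It is offered as the reason for having no long-term follow-up.

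STATISTICAL PLAN names an ANOVA for cognitive performance. The power paragraph gives its within-subject factors as treatment (real, placebo) and time (T0, T1). Period, sequence and carry-over are not named.

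**The concern.** A few hours may be enough for a stimulation after-effect to fade, but that says nothing about whether a patient still knows a word or a name a week later. If the same list and faces return, session 2 starts from a different state of knowledge than session 1.

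This can matter in three ways:

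- **Variance.** A general gain from session 1 to session 2 enters the within-patient real-minus-sham difference with opposite signs in the two sequences. Without a period term it is counted as error.
- **Ceiling.** Up to four exposures to one word list can compress later RAVLT scores and leave less room for a difference.
- **Bias.** If real stimulation helps patients learn items and those items are retained, patients who receive real stimulation first carry part of the benefit into their sham session. Randomised order and a period term remove the average practice gain but not this treatment-dependent part.

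Carry-over in a two-period crossover of 20 patients cannot be separated reliably afterwards, so the safeguard has to be in the design.

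**Working it through.** **Inputs.** From the protocol: two sessions one week apart; RAVLT at T0 and T1 of each; Face Naming once per session; 1:1 order; planned N = 20; partial η² = 0.205; α = 0.05; power 0.80; stated requirement 18. Assumed, because the documents give no value: the common practice gain π and the carried-over share k.

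**1. Counts.** RAVLT: 2 per session × 2 sessions = 4. Face Naming: 1 × 2 = 2.

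**2. The plan's own figure.** f = √(0.205/0.795) = 0.5078, as stated. N = 18 reproduces under either of two set-ups:
- four measurements and two sequence groups: λ = f²(N − 2)(3) = 0.2579 × 16 × 3 = 12.38 on 3 and 48 df, power 0.819;
- two uncorrelated measurements: λ = 2Nf² = 2 × 18 × 0.2579 = 9.28 on 1 and 17 df, power 0.819.

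The power paragraph does not say which was used.

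**3. Practice gain equal in both sequences.** With true effect d, the real-minus-sham difference is d − π in real-first patients and d + π in sham-first patients. The mean over balanced sequences is d, so there is no shrinkage. Without a period term the variance of the difference rises from 2σ² to about 2σ² + π²(20/19), where σ is the within-patient SD. At π = σ that is 3.05σ², so the SD is √(3.05/2) = 1.24 times larger. In simulation (20,000 runs, N = 20, standardised paired effect 0.5078) the mean estimate stayed at 99–100% of the true value. Power without a period term fell from 0.58 to 0.53, 0.39 and 0.23 at π = 0.5, 1.0 and 1.5 SD. With a period term it stayed at about 0.57–0.58.

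**4. Carry-over that depends on treatment, score without a T0 (Face Naming).** Let a share k of the real-session gain persist into a later sham session.
- Real-first: real − sham = d − kd.
- Sham-first: real − sham = d.
- Mean: d(1 − k/2).

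| k (assumed) | Estimate as share of d | Loss |
|---|---|---|
| 0.25 | 0.875 | 12.5% |
| 0.5 | 0.75 | 25% |

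The simulation gave about 87–88% and 75%. Adding a period term does not change this.

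**5. The same carry-over in RAVLT, analysed as T1 − T0.** In a real-first patient the retained kd is present at both T0 and T1 of the sham session. The real change is d, the sham change is kd − kd = 0, and the contrast is d. A sham-first patient also gives d. The mean is d for any k, so additive carry-over cancels. This relies on the treatment-by-time contrast being the test, and it fails if scores reach a ceiling. The documents give no expected means or score range from which to size a ceiling effect.

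**6. Power depends on the set-up.** At N = 20 with the effect multiplied by (1 − k/2):

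| Set-up | k = 0 | k = 0.25 | k = 0.5 |
|---|---|---|---|
| 1-df paired test, λ = 20 f²(1 − k/2)² | 58% | 47% | 37% |
| Set-ups that reproduce N = 18 | 86–87% | 76% | 61–63% |

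The gap between the rows is a separate question about the sample-size calculation, so neither row should be quoted as the cost of this point.

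**The case against.** The strongest case on the other side has five parts.

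- **The plan does not say that items are reused.** The Placebo group sentence can simply mean that sham sessions get the same battery as real ones. This stands. A reader might infer that identical lists and faces will be given; the documents neither say so nor rule it out. The point is that the text permits it.
- **Repetition alone does not shrink the treatment difference.** This stands (step 3). A reader might infer that any practice effect biases the result; in a 1:1 crossover it does not. Shrinkage needs unequal retention or a ceiling.
- **The pre-stimulation RAVLT score protects that outcome.** This largely stands (step 5), apart from a ceiling, where the direction of distortion is uncertain because either session's change may be compressed.
- **The face-naming mechanism is assumed.** The documents do not describe the task or say whether faces are learned in the session or already known. This stands as a limit: without new learning, k could be near zero. But the task is a primary outcome, naming is the hypothesis stated under ETHICAL CONSIDERATIONS, and there is no T0 score to absorb carry-over if it occurs.
- **Carry-over bias of this kind runs towards no effect.** True of the mechanism in step 4: it would not create a false benefit. It could still hide a real one.

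It is also tempting to read the duration sentence as the plan's reason for the one-week gap. It is not: it explains the lack of long-term follow-up, and the protocol gives no rationale for the gap.

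**Conclusion.** The point holds in conditional form. The documents establish four RAVLT and two Face Naming administrations, sessions a week apart, no call for alternate forms, and an ANOVA without a period term. Following the text literally, the same items could be reused.

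The effect on variance needs only a practice gain between sessions. The bias towards zero needs better retention after real than after sham stimulation. It applies chiefly to Face Naming, where the loss is k/2 of the true effect; k is unknown and the figures shown are a range under assumption. For RAVLT the remaining exposure is a ceiling, which cannot be sized from the documents.

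A reader might infer that the trial is certain to underestimate tACS, or that power falls to some particular low value. The documents support neither: they give no value of k, and the power figure moves with a set-up that the plan leaves unstated.

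**What to change.** Replace the sentence on tests in PROCEDURES (Placebo group) with, for example:

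> The same instruments will be used in equivalent alternative forms (a different RAVLT list at T0 and T1 of each session and a different Face Naming set in each session), with form order balanced across the two sequences.

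In STATISTICAL PLAN, add period to the ANOVA. Alternate forms deal with item-specific learning; the period term deals with general familiarity with the tasks, which new items do not remove.

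The balance needed is modest: the same mix of form orders in each sequence. With 20/2 = 10 patients per sequence, two form orders can be used for 10/2 = 5 patients each. Ten patients do not divide evenly over four list orders, but that is not required. A table of mean score by form would show whether the forms are in fact equivalent.

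The cost is sourcing equivalent lists and face sets, adding form order to the randomisation list, and one degree of freedom for period. The small downside is some form-to-form noise, which balancing keeps from biasing the treatment comparison. If alternate forms are already intended, the change is only to write them down.

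### No contact after the second session is described, so late side effects after about 10 real and 10 sham sessions have no scheduled opportunity to be reported

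*Combined protocol and SAP*

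**What the plan says.** The trial is a two-period crossover. PROCEDURES states: "After 1 week (after a single session of real stimulation or placebo stimulation) the two groups will be inverted (cross over". STUDY DESIGN gives the allocation as "tACS: placebo tACS = 1 : 1" and says that patients who start with real stimulation "will carry out a second session with placebo stimulation after 1 week and vice versa". Cognitive and TMS measures are taken before stimulation and straight afterwards, at both sessions.

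The sentence on follow-up, also in STUDY DESIGN, opens by pointing to the transience of tACS effects in general and continues: "with a duration of cognitive effects of a few hours after the interruption of stimulation, the study does not provide a long-term follow-up". No visit or call after session 2 appears anywhere in the document.

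The side effects listed in ETHICAL CONSIDERATIONS (RISK-BENEFIT) include "mild tingling sensation during or after stimulation" and "blistering at the electrode application points in more rare cases". DETECTION OF ADVERSE EVENTS consists of a duty on the principal investigator to notify the ethics committee promptly of events caused by the method. It gives no way of eliciting events, no time window and no contact point.

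**The concern.** How long an effect on cognition lasts does not settle how long side effects should be watched for. The plan's own list places at least one side effect after stimulation, and a skin reaction could plausibly be noticed only after the patient has gone home. A patient who has real stimulation first comes back a week later and has an occasion to mention it. A patient who has real stimulation second has no such occasion in the schedule. Whether a late reaction can come to light at a planned visit therefore depends on the randomised order.

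At stake is how complete the tolerability record is for a 60-minute session at 3 mA, in a study whose stated aim is to identify a possible rehabilitation protocol. Participants have mild cognitive impairment, so unprompted reporting after the last session is a weak safeguard.

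**Working it through.** The plan gives no figure for safety observation, so there is none to reproduce. The check uses the planned number of patients but not the power calculation behind it.

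**Inputs**
- 20 patients (Power analysis, under STATISTICAL PLAN).
- 1:1 order; one real and one sham session per patient, a week apart (PROCEDURES; STUDY DESIGN).
- Rate of late reactions, and the chance that one is recorded: not in the documents, so assumed below.

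**Step 1: how many sessions have a later visit.** 20 × 1/2 = 10 patients in each order.

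| Order | Patients | Session 1 (return visit at one week) | Session 2 (no later contact described) |
|---|---|---|---|
| Real, then sham | 10 | 10 real | 10 sham |
| Sham, then real | 10 | 10 sham | 10 real |

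So 10/20 = 50% of real sessions and 10/20 = 50% of sham sessions have no later scheduled visit. With the 18 patients of the power calculation the split would be 9 and 9. The method of randomisation is not stated. If it were simple randomisation, the number of real sessions coming last would have a 95% range of 6 to 14 of 20 (30% to 70%).

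**Step 2: does this favour real or sham?** Let d1 and d2 be the chances that a late event is recorded after session 1 and session 2. Let pR and pS be the chances of such an event after a real and a sham session, assumed the same in both periods. Expected recorded events are:
- real: 10·pR·d1 + 10·pR·d2 = 10·pR·(d1 + d2)
- sham: 10·pS·d1 + 10·pS·d2 = 10·pS·(d1 + d2)

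Both counts carry the same factor, so their ratio stays at pR/pS. Fewer events are seen on both sides, and neither side is favoured.

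**Step 3: illustration of what could be missed.** Take the extreme case d1 = 1 and d2 = 0, so that 10 real sessions are observed instead of 20. The chance of seeing at least one late event is 1 − (1 − p)^n:
- p = 0.05: 1 − 0.95^10 = 0.401, against 1 − 0.95^20 = 0.642
- p = 0.10: 1 − 0.90^10 = 0.651, against 1 − 0.90^20 = 0.878

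If no event is seen, the one-sided 95% upper bound on the rate is 1 − 0.05^(1/n): 0.259 for n = 10 and 0.139 for n = 20.

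The 5% and 10% rates are assumptions, and all-or-none detection is a simplification of the plan. These figures illustrate the scale of the loss; they do not estimate it.

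**The case against.** A fair defence has several parts, and most of them limit the point.

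- **The reason given may be broader than cognition.** The sentence begins with the transient effects of tACS in general. A reader might infer that the plan considered cognition alone, but the wording does not establish that. What can be said is that the only specific duration given is for cognitive effects.
- **Absence of contact is inferred.** The text excludes long-term follow-up, not every contact. Patients are followed at the clinic and could report spontaneously. The duty to notify the ethics committee has no end date, and consent pages, which might carry reporting instructions, are not in the text reviewed. The supportable statement is that no contact after session 2 is described.
- **The real-versus-sham comparison is not distorted.** Observation time is unequal within each patient, so a reader might infer bias. Step 2 shows that the shortfall is shared equally across the two orders. In addition, no comparative safety analysis is planned: the endpoints are the Face Naming Task, RAVLT and SAI.
- **Few effects are described as late.** Only tingling is explicitly placed after stimulation. That blistering might be noticed later is a reasonable reading, not the plan's statement. The plan regards the side effects overall as of little relevance.
- **The remark that similar studies are unpublished is not a safety statement.** It explains where the effect size came from, and the same sentence refers to established safety limits. It should not be read as an admission that safety data are lacking.

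What the defence does not supply is any defined window, or any planned occasion, for hearing of a late reaction after session 2.

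**Conclusion.** The point stands as a minor one. As written, the plan under-ascertains late side effects in a way that depends on treatment order. About 10 real and 10 sham sessions have no later scheduled opportunity for a report. The other 10 of each have a return visit at a week, and even that is only an opportunity, because the plan does not say that side effects are asked about at any visit.

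The split rests on 20 patients and equal allocation to the two orders. The absence of contact rests on the document as available. The primary and secondary analyses are not affected. A reader might take the drop from 64% to 40%, or from 88% to 65%, as the actual loss of detection. The documents do not support that, because they give no rate of late events and because detection is unlikely to be complete after session 1 or nil after session 2.

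**What to change.** In STUDY DESIGN, keep the decision not to follow cognition long term. There and in DETECTION OF ADVERSE EVENTS, add one short structured telephone contact after each session, at the same fixed interval both times and before the next session takes place. Existing staff can make the calls, provided the caller does not know the session type. The caller asks through the symptom list already given in ETHICAL CONSIDERATIONS. State the window in the adverse-event section, and tabulate events by session type over that equal window.

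Cost: 20 patients × 2 sessions = about 40 short calls, a one-page form and two changes of wording. No extra visit, procedure or patient is needed. The downside is a slight added burden on patients and carers.

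### The Face Naming Task, one of two primary outcomes, is described only during stimulation, so the treatment-and-time (T0, T1) model behind N = 18/20 does not fit it and the stated 80% power does not cover it

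*Combined protocol and SAP*

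**What the plan says.** The END POINTS section states that the effects of tACS "on the Face Naming Task and RAVLT will be primary outcome measures". No score is defined for the Face Naming Task.

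The task is timed in two places. PROCEDURES (Treatment group) describes a 60-minute session "during which patients will be subjected to an experimental cognitive task (Face Naming Task". STUDY DESIGN repeats it: "In both sessions, a task, the Face Naming Task, will be carried out during the stimulation with tACS, both real and placebo". STUDY DESIGN attaches pre/post testing to RAVLT and to "analysis of neurophysiological parameters of SAI by TMS before treatment and immediately after", but not to the naming task.

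STATISTICAL PLAN says only that an ANOVA will be used for cognitive performance. The power paragraph takes a partial eta-squared of 0.205 (f(V) = 0.5078), alpha 0.05 and power 0.80. It reaches 18 subjects from a repeated-measures ANOVA whose within-subject factors are "both treatment (real vs placebo - crossover study) and time (T0 and T1". It names no outcome and ends: "The proposed sample size of 20 subjects should be adequate to achieve the main objective of the study".

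**The concern.** A treatment-by-time model needs a T0 and a T1 value in each session. As described, the Face Naming Task supplies neither. An ANOVA of real against sham can still be run on it, but the plan gives no score, model or power for that analysis.

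This matters because ETHICAL CONSIDERATIONS frames the cognitive hypothesis in terms of naming: "We hypothesize that tACS can have a positive effect on naming performances". The Face Naming Task is the only naming outcome. A reader who accepts the 80% figure could take a null naming result as evidence of no effect, when the trial may have had much less chance of detecting one.

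A second question is whether learning between the two visits distorts the comparison, since the plan mentions no period term.

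**Working it through.** **Inputs.** From the power paragraph: partial eta-squared 0.205, f(V) 0.5078, alpha 0.05, power 0.80, N = 18 calculated and 20 proposed. From STUDY DESIGN: 1:1 allocation, two sessions one week apart. Assumed, because not stated: two-sided testing, sphericity, one naming score per session, and that 0.205 carries over to the naming contrast.

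**Effect size.** f² = 0.205 / (1 − 0.205) = 0.2579, so f = 0.5078. This matches the plan.

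**Reproducing N = 18.** Take four measurements per patient (2 treatments × 2 times) and k groups. Then df1 = 3, df2 = 3(N − k) and λ = 3(N − k)f², with power from the noncentral F distribution.
- Two sequence groups, N = 17: λ = 3 × 15 × 0.2579 = 11.60, power 0.789.
- Two sequence groups, N = 18: λ = 3 × 16 × 0.2579 = 12.38, power 0.819. So 18 is the smallest N that reaches 80%.
- One group: 17 is enough (power 0.819), and 18 gives 0.846.

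Either way, the stated figure comes from a 3-df test on four measurements. The 1-df versions do not give 18.

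**The naming task.** One score per session gives two values per patient and a 1-df contrast. The f(V) convention for λ varies, so all versions are shown for N = 20:

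| λ | df2 | λ at N = 20 | Power at N = 20 | N for 80% | Partial eta-squared needed for 80% at N = 20 |
|---|---|---|---|---|---|
| N f² | 19 | 5.16 | 0.577 | 33 | 0.304 |
| N f² | 18 | 5.16 | 0.575 | 33 | 0.305 |
| (N − 1) f² | 19 | 4.90 | 0.556 | 34 | 0.315 |
| (N − 2) f² | 18 | 4.64 | 0.531 | 35 | 0.328 |

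The row with λ = (N − 2)f² matches the two-group convention that reproduces 18.

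**As a standardised difference.** The within-patient difference in SDs of the differences is d_z = √(λ/N). At N = 20, 0.205 implies √(4.64/20) = 0.48 to √(5.16/20) = 0.51. For 80% power d_z must be about 0.66 (0.660 with 19 df, 0.662 with 18 df).

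**RAVLT.** It is measured before and after in both sessions, so the T0/T1 structure fits. Its treatment-by-time interaction is still a single contrast with 1 df, so at the same f(V) the table applies to it as well.

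**Learning between visits.** A shift of L from visit 1 to visit 2 adds +L to the real-minus-sham difference in one sequence and −L in the other. With 10 patients per sequence these cancel in the mean but widen the spread of the differences. Simulation (200,000 runs, true d_z 0.508; L is assumed, in SDs of the within-patient difference):

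| L | Power, no period term | Power, period term |
|---|---|---|
| 0 | 0.58 | about 0.58 |
| 0.25 | 0.55 | about 0.58 |
| 0.5 | 0.48 | about 0.58 |
| 1.0 | 0.26 | about 0.58 |

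The mean estimate stays at 0.507–0.509 throughout, so there is no bias, only lost power.

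**The case against.** The strongest reply is that two problems are being joined. The timing of the naming task is a gap in description. The 53–58% comes from setting a 3-df calculation against a 1-df contrast, which affects RAVLT equally, and adding a pre-stimulation naming test would not by itself restore 80%. That is correct. It limits what is special to the naming task, but it does not rescue the 80% figure for either outcome.

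Other points stand as limits:
- One score per session is an inference. A 60-minute session could hold early and late scores, and the plan never defines T0 and T1. The schedule should settle this.
- The 0.205 comes from studies that the plan says differ in population and stimulation method, and their outcome is not named. The power percentages are therefore illustrative. If 0.205 does not apply to naming, the plan has no power basis for that outcome at all.
- The learning shifts have no source in the plan, an unspecified ANOVA does not exclude a period term, and at 0.25 SD or less the loss is only 2–3 percentage points.
- The sentence on naming is a general one that also covers frontotemporal dementia. The stated aim is cognitive performance, which RAVLT also serves.

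PROCEDURES also mentions pre- and post-stimulation effects in general terms, but the same sentence then specifies RAVLT and SAI. The one-week repetition is the second crossover session and creates no pre/post pair.

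**Conclusion.** The concern holds. The certain part needs no assumed effect size: as the task is described, the plan's only power calculation uses a structure that the Face Naming Task lacks, so the 80% was not derived for this primary outcome.

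The size is conditional. With one score per session and 0.205 applied to the 1-df contrast, power at 20 patients is 53–58%, and 80% would take 33–35. Put the other way, 20 patients give 80% power only for partial eta-squared of about 0.30–0.33. The shortfall extends to the RAVLT interaction. Visit effects do not bias the comparison under balanced sequences, but omitting a period term could lower power further. This should be fixed.

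**What to change.** 1. State whether the Face Naming Task is given only during stimulation, and name in advance the one score per session to be analysed. If T0 and T1 scores are intended, put them in the schedule.
2. If it is given only during stimulation, analyse that score real versus sham, with treatment and period as fixed effects, patient as a random effect, and no time factor.
3. Keep the treatment-by-time or baseline-adjusted analysis for RAVLT and SAI, also with a period term.
4. Replace the 80% statement with the power or detectable difference at N = 20 for the 1-df contrast of each primary outcome, and say which outcome and contrast the assumed effect size describes. The 80% figure should not be kept for RAVLT either.

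The cost is SAP wording and a less favourable power figure. No new data or visits are needed unless the sponsor chooses to enlarge the sample.
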